**Which Committee will review this protocol?**

The Clinical Research Committee - (CRC)

## Protocol Body

### 1.0 Objectives

1. To determine the efficacy of Letrozole plus Imatinib Mesylate in patients with ER and or PgR positive metastatic breast cancer. Efficacy will be measured by the rate of clinical tumor response.
2. To determine the safety and tolerability of Letrozole plus Imatinib Mesylate in patients with metastatic breast cancer.
3. To determine the time to disease progression and overall survival in patients with metastatic breast cancer who are treated with Letrozole plus Imatinib Mesylate.

### 2.0 Background

#### 2.1 Metastatic Breast Cancer

Breast cancer is the most common malignant disease in women and the second leading cause of female cancer death. Approximately 200,000 women are yearly diagnosed with breast cancer and over 40,000 patients die from breast cancer in the United States.

Although patients with early-stage breast cancer can be cured by surgery, radiation and systemic therapy, once the disease has spread to distant organs it is not curable by conventional therapies. Patients with metastatic disease whose tumors spread the estrogen receptor (ER) or the progesterone receptor (PR) can be effectively palliated using a range of endocrine therapies. These include tamoxifen and aromatase inhibitors. Chemotherapy is reserved for patients with hormone-insensitive or hormone-resistant metastatic breast cancer. Endocrine and chemotherapeutic agents are also not curative in most patients with late stage breast cancer, in part because women who progress to stage IV often become refractory to hormonal therapy and chemotherapy. Consequently, patients with refractory stage IV disease are often treated primarily with palliative intent.

The median survival of patients with stage IV breast cancer is approximately two years. However, the outlook for survival in stage IV patients who have failed at least one chemotherapy regimen is often fewer than 12 months. Due to the limited treatment options available for patients with refractory stage IV breast cancer, and the poor prognosis for this disease population, it is clear that new therapeutic options for treatment should be investigated.

#### 2.2 Letrozole

Letrozole molecular weight is 285.31. It is freely soluble in dichloromethane, slightly soluble in ethanol, and practically insoluble in water. In human liver microsomes, letrozole strongly inhibits the cytochrome P450 (CYP) isoenzyme 2A6 (CYP 2A6) and moderately inhibits the CYP isoenzyme 2C19 (CYP 2C19). Letrozole has not been shown to affect synthesis of adrenal corticosteroids, aldosterone, or thyroid hormones. Rapidly and completely absorbed. Absorption is not affected by food. The volume of distribution (Vol D) is approximately 1.9 liters per kg of body weight. It is biotransformed in the liver, by the CYP isoenzymes 3A4 and 2A6 (CYP 3A4 and CYP 2A6), to an inactive carbinol metabolite and its ketone analog. Its half life is approximately 2 days. Time to steady-state concentration in the plasma is 2 to 6 weeks. Letrozole is eliminated renally, approximately 90% of a dose (approximately 75% as the glucuronide conjugate of the inactive metabolite, 9% as two unidentified metabolites, and 6% unchanged). Letrozole does not go under any metabolism through the CYP450.

Letrozole (4,4'-(1H-1,2,4-Triazol-1-ylmethylene)bis-benzonitrile) is a synthetic achiral benzyltriazole derivative. It is an orally active highly selective non-steroidal competitive inhibitor of the aromatase enzyme system. Aromatase inhibitors block the aromatase enzyme, consequently lowering estrogen

levels and thereby deprive the tumor of its growth stimulus. Letrozole effectively inhibits the conversion of androgens to estrogens in both *in vitro* and *in vivo*. This property makes it in particular suitable for postmenopausal women whose main source of estrogen is via peripheral aromatization of androgen precursors.

Letrozole is up to 150-250 times more potent than the first generation aromatase inhibitor Aminoglutethimide (AG), *in vitro* and more than 10,000 times as potent as AG in inhibiting aromatase *in vivo*. The high potency of Letrozole is not accompanied by any significant effect on adrenal steroidogenesis *in vitro* or *in vivo* over its maximally effective dose range. Inhibition of adrenal steroidogenesis resulting in adrenal hypertrophy does occur with therapeutic doses of AG. The high potency and selectivity of Letrozole explains its pharmacological profile and high therapeutic index.

In postmenopausal patients with advanced breast cancer, daily doses of 0.1 to 5 mg Letrozole suppressed plasma levels of estradiol, estrone and estrone sulfate to 75-95% from baseline. A study done in postmenopausal breast cancer patients comparing Letrozole to Anastrozole concluded that Letrozole suppresses plasma estrogen levels more completely than Anastrozole. Letrozole was statistically superior to Anastrozole in reducing plasma levels of both estrone sulfate (p=0.019) and estrone (p=0.0037). Patients switching from 6 weeks' Anastrozole to 6 weeks' Letrozole consistently achieved further estrogen suppression. Conversely, patients switching from 6 weeks' Letrozole to 6 weeks' Anastrozole experienced an increase in estrogen plasma levels.

### **2.2.1 Clinical Experience with Letrozole**

A Phase III global, multicenter, randomized clinical trial evaluated Letrozole (2.5 mg/day) as a first line hormonal therapy as compared to the present standard of treatment, tamoxifen (20 mg once daily). This trial accrued 907 postmenopausal women with ER and/or PR positive or unknown receptor breast cancer and locally advanced disease, metastatic disease, or loco-regional recurrence not amenable to treatment by surgery or radiotherapy. Patients received treatment until disease progression or discontinuation for any other reason.

The primary endpoint was time to disease progression. Letrozole was superior to tamoxifen in TTP, reducing the risk of progression by 30% [hazard ratio 0.70, 95% confidence interval 0.60 to 0.82, P=0.0001, Cox regression], with median time to progression 41 weeks for Letrozole and 26 weeks for tamoxifen. Fewer patients progressed on Letrozole (69%) than on tamoxifen (77%). Secondary endpoints included overall tumor response rate, clinical benefit, and time to treatment failure. Overall tumor response rate (complete and partial response) was significantly higher with Letrozole (30%) than with tamoxifen (20%) (odds ratio 1.71, 95% confidence interval 1.26 to 2.31, P=0.0006, Mantel-Haenszel) with higher response rates seen irrespective of dominant site of disease. Clinical benefit (CR, PR or stabilization of disease lasting at least 24 weeks) was significantly superior for Letrozole as compared to tamoxifen [P=0.001, Mantel-Haenszel]. Time to treatment failure (P=0.0001, Cox regression) was significantly superior for Letrozole compared to tamoxifen. At the time of the analysis cutoff, 178 patients remain in the core portion of the trial (111 patients on Letrozole and 67 patients on tamoxifen).

Tolerability was similar in both arms of the trial, with 2% of patients on Letrozole and 3% of patients on tamoxifen discontinuing core therapy due to adverse events. In conclusion, Letrozole has a highly favorable toxicity profile and is superior in TTP and CR compared to tamoxifen in patients with locally advanced and metastatic breast cancer. Based on this study and other supportive data, FDA approved Letrozole for first-line hormonal therapy in locally advanced or metastatic breast cancer in January 2001.

A recently completed randomized, double-blind, multicenter study comparing the efficacy of 4 months of therapy with Letrozole and tamoxifen as primary treatment in the pre-operative setting, confirms the superior efficacy of Letrozole over tamoxifen. Response rate assessed by clinical palpation (primary endpoint) was 55% for Letrozole compared to 36% for tamoxifen (p<0.001). Response rates were similarly significant in favor of Letrozole when assessed by ultrasound or mammography.

## 2.3 Imatinib mesylate (Gleevec)

Imatinib mesylate (Gleevec) is a phenylaminopyrimidine derivative and is a member of a new class of drugs collectively known as signal transduction inhibitors. More specifically, it is an inhibitor of several protein-tyrosine kinases that are believed to play a role in the proliferation of tumor cells. These include the tyrosine kinases associated with Bcr-Abl, the PDGF-R and c-Kit. Because these kinases are either uniquely or preferentially expressed in tumor cells, it is reasoned that the use of compounds causing inhibition of these targets may result in fewer or less debilitating side effects than those associated with standard anti-cancer chemotherapy.

The Bcr-Abl fusion protein, with enhanced tyrosine kinase activity, is an end product of a reciprocal translocation between chromosomes 9 and 22, replacing the first exon of *c-abl* with sequences from the BCR gene Bcr-Abl fusion protein. Bcr-Abl expression can induce a disease resembling CML in mice, and the tyrosine kinase domain of the molecule is essential for leukemic transformation. These observations provide evidence that the Bcr-Abl protein is a major factor in the pathogenesis of CML and indicate that inhibition of the Bcr-Abl kinase is a rational therapeutic target for the treatment of CML.

PDGF is a ubiquitous growth factor driving cell proliferation during normal development and in a variety of pathological conditions. The PDGF-dependent mitogenic pathway has been implicated in pathological conditions including cancer and connective tissue disorders. Interest in the role of PDGF in cancer stems from the finding that the transforming protein of the simian sarcoma retrovirus (*v-sis* oncogene product) is highly related to the B-chain of PDGF (c-sis proto-oncogene product). Expression of the *v-sis* or *c-sis* genes in cells expressing the PDGF receptor has been shown to cause cellular transformation and tumorigenicity *in vivo*. Dysregulation of PDGF-R signaling in tumors can lead to either autocrine or paracrine stimulation of cell growth. The PDGF-R pathway has been implicated in the growth of tumors of mesenchymal origin, most notably sarcomas and gliomas.

SCF is thought to play a central role in the proliferation and differentiation of stem cells. SCF synergizes with other growth factors to stimulate formation of both differentiated progenitor cells and primitive multi-lineage progenitor cells of the myeloid and erythroid lineages. Dysregulation of SCF receptor signaling has been implicated in some human cancers including SCLC, breast cancer, acute myeloid leukemia (AML), glioma, testicular and gynecological cancers. c-Kit and SCF over-expression is seen in most SCLC cell lines and primary tumors, raising the possibility of an autocrine loop. In GIST and mastocytosis mutations in *c-kit* resulting in ligand-independent constitutive activation of the receptor have been reported.

Accumulating evidence for the involvement of protein-tyrosine kinases in human proliferative disorders has led to a search for specific inhibitors. Imatinib Mesylate has been identified as a potent inhibitor of the Bcr-Abl tyrosine kinase at the *in vitro*, cellular and *in vivo* level. Furthermore, the compound inhibits PDGF- and SCF-mediated cellular events. These findings provided a cogent rationale for testing imatinib in human cancers where dysregulation of these pathways may contribute to malignant growth.

### 2.3.1. Clinical Experience with Imatinib Mesylate

#### Pharmacokinetics

The pharmacokinetics of Imatinib Mesylate have been evaluated in healthy subjects and in population pharmacokinetic studies in over 900 patients. Imatinib is well absorbed after oral administration with  $C_{max}$  achieved within 2-4 hours post-dose. Mean absolute bioavailability for the capsule formulation is 98%. Following oral administration in healthy volunteers, the elimination half-lives of imatinib and its major active metabolite, the N-desmethyl derivative, were approximately 18 and 40 hours, respectively. Mean imatinib AUC increased proportionally with increasing dose in the range 25mg - 1000mg. There was no significant change in the pharmacokinetics of imatinib on repeated dosing, and accumulation is 1.5-2.5 fold at steady state when Imatinib Mesylate is dosed once daily. At clinically relevant concentrations of imatinib, binding to plasma proteins in *in vitro* experiments is approximately 95%, mostly to albumin and a

$\alpha$ -acid glycoprotein. CYP3A4 is the major enzyme responsible for metabolism of imatinib. Other cytochrome P450 enzymes, such as CYP1A2, CYP2D6, CYP2C9, and CYP2C19, play a minor role in its metabolism.

### Chronic Myeloid Leukemia

Proof of activity was first obtained in a phase I clinical trial in patients with chronic and acute Philadelphia chromosome-positive (Ph+) leukemias. This was followed by phase II studies in Ph+ leukemias as well as patients with a range of solid tumors.

Three international, open-label, single-arm Phase 2 studies were conducted to determine the safety and efficacy of Imatinib Mesylate in patients with Ph+ CML: 1) in the chronic phase after failure of Interferon (IFN) therapy, 2) in accelerated phase disease, or 3) in myeloid blast crisis. Doses administrated and efficacy results are shown in Table 1.

**Table 1 Response in CML studies**

	Chronic Phase IFN Failure (N=532) 400 mg	Accelerated Phase (N=181) 400mg n=62 600mg n=119	Blast Crisis (N=229) 400mg n=37 600mg n=223
Cytogenetic response			
Major	60%	24%	16%
Complete	41%	17%	7%
Partial	19%	7%	9%
Minor	5%	7%	2%
Minimal	11%	17%	13%
Complete hematologic response	95%	53%	15%
No evidence of leukemia		10%	9%
Return to chronic phase		19%	28%

**Cytogenetic response criteria:** complete (0% Ph+ metaphases), partial (1-35%), minor (36-65%) or minimal (66-95%). A major response (0-35%) combines both complete and partial responses.

Imatinib Mesylate is indicated for the treatment of patients with Philadelphia chromosome positive (Ph+) chronic myeloid leukemia (CML) in blast crisis, accelerated phase, or in chronic phase after failure of interferon-alpha therapy.

### Chronic Phase, Newly Diagnosed

An open-label, multicenter, randomized phase III study of Interferon vs. ST1571 (IRIS) has been conducted in patients with newly diagnosed Ph+ CML within 6 months of their initial diagnosis. In the Imatinib Mesylate arm, patients were treated with 400mg daily. In the IFN arm, patients were treated with a target dose of IFN of 5 MIU/m^2/day subcutaneously in combination with subcutaneous Ara-C 20 mg/m^2

/day for 10 days/month. A total of 1106 patients have been randomized. An interim analysis done at the time when all patients had a minimum follow-up of 12 months was presented at the ASCO 2002 Meeting (Abstract #1). Response data are shown in Table 2. Complete hematologic response, major cytogenetic response and complete cytogenetic response were significantly higher in the Imatinib Mesylate arm compared to the IFN + Ara-C arm.

**Table 2 Response in newly diagnosed CML (IRIS Study)**

	Imatinib Mesylate	IFN+Ara-C
(Best response rates)	n=553	n=553
Hematologic response		
CHR [95% CI]	94.4%* [92.1%, 96.2%]	54.6%* [50.4%, 58.8%]
Cytogenetic response		
Major response [95% CI]	82.6%* [79.2%, 85.7%]	20.3%* [17.0%, 23.8%]
Complete CyR n (%)	67.8%*	7.4%*
Partial CyR n (%)	14.8%	12.8%

\* p<0.001, Fisher's exact test

**Hematologic response criteria (all responses to be confirmed after 4 weeks):**

WBC<10 x10^9/L, platelet <450 x10^9/L, myelocyte + metamyelocyte <5% in blood, no blasts and promyelocytes in blood, basophils<20%, no extramedullary involvement

**Cytogenetic response criteria:** complete (0% Ph+ metaphases), partial (1-35%), minor (36-65%) or minimal (66-95%). A major response (0-35%) combines both complete and partial responses.

## 2.4 Rationale for Study

Targeted therapy offers the promise of reduced toxicity by targeting specific well-defined pathways. The estrogen receptor (ER) is one of the best characterized targets for breast cancer therapy. Successful ER-directed approaches include antiestrogens and aromatase inhibitors. A randomized phase III clinical trial showed that Letrozole is superior to tamoxifen as first-line therapy for metastatic breast cancer. Overall, 49% of patients treated with Letrozole had an objective response or were stable for longer than 6 months. However, half of the patients did not respond to Letrozole despite expressing estrogen and/or progesterone receptors. The mechanisms of resistance to endocrine therapy are complex and not well defined. One such mechanism involves the overexpression of tyrosine kinase receptors such as EGFR and HER-2. C-kit, a 145-kd transmembrane glycoprotein, is a member of tyrosine kinase subclass III. It is structurally related to other receptors of the same family; those include platelet-derived growth factor (PDGF), macrophage colony-stimulating factor, and flt-3 ligand. The c-kit gene product is expressed in hematopoietic progenitor cells, mast cells, germ cells and some solid tumors including breast cancer. In some types of tumors, inhibition of c-kit activity reduces cellular proliferation, suggesting a role for the use of pharmacological inhibitors of c-kit in the treatment of c-kit dependent malignancies. Kit is expressed at high levels in normal breast ductal epithelial cells. Expression of c-kit protein has been demonstrated in 10% to 20% by immunohistochemical staining; c-kit mRNA has been detected in 80% of primary breast tumors in one study. Studies have also shown that co expression of c-kit and its ligand, stem cell factor (SCF), is seen in the majority of surgical breast tumor specimens as well as in the

majority of established breast tumor cell lines. In particular, MCF-7 cells (that naturally express ER and SCF) transfected with a c-kit expression vector exhibit enhanced growth in serum-free medium supplemented with IGF-1 and EGF. Preliminary investigations suggest that co expression of SCF and kit may be involved in the response to erbB ligands through activation of MAPK and PI3K.

Platelet-derived growth factor (PDGF) is composed of two chains, A and B, held together by disulfide bonds and present in three dimeric forms AA, AB, BB. The dimers bind to two receptor types:  $\alpha$  and  $\beta$ . The  $\beta$  receptor has a ligand-activated protein kinase. Platelet-derived growth factor (PDGF) is secreted by most human breast carcinoma cells; PDGF has been demonstrated in malignant breast tissue and mostly localized in the periepithelial stroma. Recent studies of plasma and tissue PDGF concentrations in breast patients indicated that PDGF levels predict for shorter survival times and a lower response to chemotherapy.

Imatinib Mesylate is a known inhibitor of the c-abl, bcr-abl, PDGF receptor and c-kit kinase activity. Imatinib Mesylate showed antitumor activity in the syngeneic BN-472 rat breast carcinoma model. When administered at 50mg/kg/ twice daily for four weeks, the compound inhibited primary tumors transplanted orthotopically and reduced the incidence and severity of metastatic disease. This drug is presently being investigated in hematological malignancies as well as solid tumors.

As mentioned previously, abnormalities in growth factor signaling pathways may account for the endocrine-resistant phenotype and thus may represent a target for new therapies to overcome endocrine resistance and enhance clinical response rate. For example growth factor signaling via tyrosine kinase growth factor receptor family (EGFR and HER2) may be up-regulated during endocrine treatment and thus allowing cells to grow in a hormone-independent manner. In lines with that, it was shown that the EGFR tyrosine kinase inhibitor ZD-1839 blocked tyrosine kinase activity and profoundly inhibited cell growth in Tamoxifen resistant MCF-7 breast cancer cells.

A recent study demonstrated that Letrozole induces high response rates in breast cancer patients, especially in those tumors which express higher levels of the tyrosine kinase receptors (Erb-B1 (EGFR) and Erb-B2 (Her-2/neu)). Preclinical studies have shown that hormone-resistant MCF-7 breast cancer cells with up-regulated tyrosine kinase signaling, had maximal growth inhibition and significantly delayed time to disease progression when they were treated with tyrosine kinase inhibitors in combination with antiestrogen agents. Therefore blockage of the estrogenic activity pathway and the tyrosine kinase pathway might not only have additive effects, but might also, by overcoming hormonal resistance caused by tyrosine kinase activity, synergistic effects. The aim of this study is to evaluate the efficacy and safety of Imatinib Mesylate in combination with Letrozole in patients with ER and /or PgR positive and C-kit and/or PDGFR positive metastatic breast cancer.

## **3.0 Study Design**

This is a single-institution phase II study of once daily doses of Letrozole 2.5 mg and Imatinib Mesylate 400 mg administered orally twice a day in postmenopausal women with hormone-sensitive metastatic breast cancer. Even though no overlapping toxicity from the combination is expected, the starting dose for Imatinib Mesylate will be 300 mg twice a day for the first 3 patients and will be escalated up to 400mg twice a day within the same patient after 2 weeks. The dose of Letrozole will remain stable at 2.5 mg daily. If no toxicity occurs, subsequent patients will continue to start at 800 mg daily dose of Imatinib Mesylate as outlined in section 5.0.

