## **5.0 Treatment Plan**

### **5.1 Phase I Part**

The first 3 patients will be started at a dose of 300 mg Imatinib Mesylate twice a day and the dose will be escalated to 400 mg twice a day after 2 weeks in the same patient if no toxicity occurs. If grade 3/4 toxicity is observed, the dose of Imatinib Mesylate will be reduced as outlined in section 6.2 and 6.3 and the subsequent patients will be treated at that dose levels. The dose for Letrozole will be 2.5 mg, per oral, given once a day.

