### **5.2 Phase II Part**

The dose for Imatinib Mesylate will 400 mg, twice a day (total daily dose 800 mg), per oral. Imatinib Mesylate is a local irritant and must be taken in a sitting position with a large (250 mL) glass of water. (Direction of use on medication label: Take as directed with a large glass of water). Imatinib Mesylate should not be taken with grapefruit juice.

The dose for Letrozole will be 2.5 mg, once a day, per oral.

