## **6.2 Dose Modifications for Non-Hematological Toxicity**

### **Grade 2**

If the patient experiences a Grade 2 non-hematologic toxicity, study drug must be withheld until the toxicity has resolved to  $\leq$  Grade 1. Imatinib Mesylate may then be resumed at the same daily dose. If the Grade 2 toxicity recurs, Imatinib Mesylate must be withheld until the toxicity has resolved to  $\leq$  Grade 1, and the daily dose must be reduced to 400 mg for patients receiving 600mg of Imatinib Mesylate or to 600mg for patients receiving 800mg of Imatinib Mesylate.

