### **Grade 3/4**

If the patient experiences Grade 3/4 toxicity study drug must be withheld until the toxicity has resolved to  $\leq$  Grade 1 and the daily dose must be reduced to 400mg for patients receiving initially 600mg of Imatinib Mesylate or to 600 mg for patients receiving 800 mg. If the Grade 3/4 toxicity recurs, Imatinib Mesylate must be withheld until the toxicity has resolved to  $\leq$  Grade 1, and the daily dose must be reduced to 300mg once daily for patients receiving 400mg of Imatinib Mesylate or to 400mg daily for patients receiving 600mg of Imatinib Mesylate.

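### Sections 3.0 and 5.1 use different toxicity triggers for later patients' starting dose, and no section requires any observation at 800 mg/day before patient 4 starts

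*Combined protocol and SAP*

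**What the plan says.** **Starting dose of later patients.** Section 3.0: "If no toxicity occurs, subsequent patients will continue to start at 800 mg daily dose of Imatinib Mesylate as outlined in section 5.0". It gives no dose for the case where some toxicity does occur. Section 5.1 works from the other side: "If grade 3/4 toxicity is observed, the dose of Imatinib Mesylate will be reduced as outlined in section 6.2 and 6.3". For everyone who enters after such an event, its rule is that "the subsequent patients will be treated at that dose levels". Section 5.2 attaches no toxicity condition: "The dose for Imatinib Mesylate will 400 mg, twice a day (total daily dose 800 mg), per oral".

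**Escalation within the first three patients.** In 3.0 the dose "will be escalated up to 400mg twice a day within the same patient after 2 weeks", with no condition in that sentence. In 5.1 "the dose will be escalated to 400 mg twice a day after 2 weeks in the same patient if no toxicity occurs".

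**Individual dose changes.** Section 6.2: "If the patient experiences a Grade 2 non-hematologic toxicity, study drug must be withheld until the toxicity has resolved to" grade 1 or lower. After a grade 3/4 non-hematological event the daily dose is "reduced to 400mg for patients receiving initially 600mg of Imatinib Mesylate or to 600 mg for patients receiving 800 mg". Under 6.3, a first grade 3/4 neutropenia or thrombocytopenia that resolves within two weeks allows the same dose to be resumed. If it recurs or lasts longer, the dose falls. Anemia leads to no reduction.

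**Timing.** Section 13.0 expects 2 patients per month. Section 7.1 schedules laboratory tests at weeks 1, 2, 3, 4, 6 and 8, and the first on-treatment examination at month 1 (week 4 in Table 7). The only interval attached to the first three patients is the two weeks at 600 mg/day.

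**The concern.** The first three patients are there to check 800 mg/day of imatinib with letrozole before others start at that dose. Two features weaken that check.

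First, the text does not settle what happens after mild toxicity. Mild toxicity is what the protocol's own safety section leads one to expect: under GIST, section 6.0 reports that almost every patient had at least minor adverse events. A reader who applies 3.0 literally would not start patient 4 at 800 mg. A reader who applies 5.1 and 5.2 would. Similarly, a grade 1 event in the first two weeks blocks escalation under 5.1 but not under 3.0, so it is unclear which of the first three patients ever reach 800 mg.

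Second, nothing ties the start of patient 4 to experience at 800 mg/day. At the planned accrual rate the third patient may have contributed almost nothing at the target dose by then.

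At stake are the starting dose of patient 4 and those who follow, and whether the run-in informs it.

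**Working it through.** The documents give no figure for this point, so there is none to reproduce. The check has three parts.

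**1. The two triggers side by side, by worst toxicity in the first three patients**

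| Worst toxicity | Section 3.0 | Section 5.1 | Section 5.2 |
|---|---|---|---|
| None | 800 mg/day | no reduction | 800 mg/day |
| Grade 1/2 only | condition for 800 mg not met; no dose given | no reduction | 800 mg/day |
| Grade 3/4 | condition for 800 mg not met; no dose given | reduced dose from 6.2 or 6.3, if they require one | 800 mg/day, no link to the run-in |

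Only the middle row is unsettled. In the last row 5.1 supplies the rule, and where 6.3 requires no reduction, none passes on.

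**2. How often the literal condition in 3.0 would be met**

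With a per-patient probability *a* of any toxicity, the chance of none in three patients is (1 − *a*)³. Table 5 (GIST, 400–600 mg) gives related events of any grade in 97–99% of patients, 98% overall:

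- *a* = 0.97: 0.03³ = 0.000027
- *a* = 0.98: 0.02³ = 0.000008
- *a* = 0.99: 0.01³ = 0.000001

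Table 5 covers a different disease, lower doses and probably longer follow-up. With lower assumed rates:

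- *a* = 0.50: 0.5³ = 0.125
- *a* = 0.20: 0.8³ = 0.512

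At Table 5 rates the literal condition would almost never release the planned phase II dose. Even at 20% it would do so only about half the time.

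**3. Exposure at 800 mg/day when patient 4 is due**

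Inputs: 2 patients per month (section 13.0), escalation at day 14 (sections 3.0 and 5.1), and, as assumptions, even spacing and a month of 30.44 days. Spacing = 30.44 / 2 = 15.22 days, so patient 4 is due on day 3 × 15.22 = 45.7.

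Days at 800 mg = 45.66 − start day − 14:

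- Patient 1 (day 0): 31.7
- Patient 2 (day 15.22): 16.4
- Patient 3 (day 30.44): 1.2

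The total is 49.3 patient-days. Patient 3 is escalated on day 30.44 + 14 = 44.4. Her next laboratory tests (week 3) fall on day 30.44 + 21 = 51.4 and her first on-treatment examination (week 4) on day 30.44 + 28 = 58.4. Both come after patient 4 is due.

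Patient 3's exposure is simply the gap between patients 3 and 4 less 14 days. A gap under 14 days gives none. At 1 patient per month the three exposures are about 77, 47 and 16 days.

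**Cost of a hold**

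- 14 days at 800 mg ends at patient 3's week 4 visit, day 58.4. Delay = 58.44 − 45.66 = 12.8 days. Exposures become 44.4, 29.2 and 14.0 days.
- 28 days at 800 mg ends at her week 6 laboratory visit, day 30.44 + 42 = 72.4. Delay = 72.44 − 45.66 = 26.8 days. Exposures become 58.4, 43.2 and 28.0 days.

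**The case against.** The strongest reply is that the two sections do not contradict each other. Section 3.0 states one case, gives no dose for any other, and sends the reader to section 5.0. There, 5.1 reduces only for grade 3/4 toxicity and 5.2 sets 800 mg. Read together they point to 800 mg after grade 1/2 toxicity, and the near-impossibility of the literal 3.0 condition at Table 5 rates supports that reading. The different escalation sentences can likewise be read as a summary and its detail. This is largely right: 3.0 is silent rather than contrary. What remains is that its only stated condition for 800 mg is one that the expected course of events will not satisfy, and a dosing rule should not need to be inferred.

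On observation, both conditional sentences imply that someone looks at the first three patients. Laboratory tests are frequent to week 8, adverse events can be reported between visits, and the grade 3/4 rule in 5.1 has no cut-off, so a late event still lowers later doses. Sections 6.2 and 6.3 act on every patient. All of that stands, and it limits the harm to the few patients who start early. It does not supply a required period at 800 mg/day. The figure of about 1 day for patient 3 does depend on even accrual at the planned rate.

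A reader might also calculate how often three patients would show some toxicity but none of grade 3/4, and present that as the chance of a wrong dose. The documents do not support this. It would be the chance of reaching a case that has a likely reading, and the rates would be borrowed from another disease or assumed.

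**Conclusion.** The point holds as a gap in the dosing text with limited consequences. The triggers in 3.0 and 5.1 differ, grade 1/2 toxicity alone falls between them, and the escalation sentences differ as well. No section requires any observation at 800 mg/day before patient 4 starts. At an even 2 patients per month, with escalation on day 14, the first three have about 32, 16 and 1 days at that dose when patient 4 is due, and patient 3 has had no scheduled laboratory test or examination since escalation. Slower accrual eases this; a shorter gap between patients 3 and 4 worsens it.

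A reader might infer that later patients would be treated at an unsafe dose without protection. The documents do not support that, given the open-ended rule in 5.1 and the individual rules in 6.2 and 6.3. The change should be made because it is cheap and lets the run-in do its job.

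**What to change.** 1. **Section 3.0.** Limit the condition for later patients to: *no grade 3/4 toxicity in the first 3 patients*. Make the escalation sentence read *as set out in 5.1*.
2. **Section 5.1, escalation.** Escalate after two weeks unless the patient has had toxicity for which 6.2 or 6.3 requires the drug to be withheld (grade 2 or higher non-hematological; grade 3/4 neutropenia or thrombocytopenia).
3. **Section 5.1, hold.** Patient 4 does not start until the first three have been assessed after a stated period at 800 mg/day, at minimum 14 days, ending at the existing week 4 laboratory tests and examination.
4. **Section 5.1, inherited dose.** If 6.2 or 6.3 requires a dose reduction after a grade 3/4 event in one of the first three, later patients start at that reduced dose. A first hematological event that resolves within two weeks does not lower it, nor does anemia.
5. **Lower-grade intolerance.** Any of the first three who cannot be escalated, or who is reduced for lower-grade toxicity, is counted and reviewed before patient 4 starts. She should not be replaced without limit, since that would select tolerant patients.

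**Cost.** Wording in two sections, no new visits, and one delay of about 13 days at 2 per month. If accrual is otherwise continuous, 45 / 2 = 22.5 months becomes 22.5 + 12.8 / 30.44 = 22.9. At 1 per month there is no delay, because the 30-day gap already exceeds the 28 days needed. A 28-day period costs about 27 days (22.5 + 26.8 / 30.44 = 23.4 months). The length beyond 14 days is the sponsor's choice. Days on which the drug is withheld would lengthen the hold if they are not counted.
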